# **List of Abbreviations**

AE Adverse event

ADE Adverse device effect
ANCOVA Analysis of covariance

BMI Body mass index

CE mark Certification mark that indicates conformity of the product with the

requirements of the applicable European Community directives

CI Confidence interval

CIS Checklist Individual Strength

CRF Case report form

CRO Contract research organization

eCRF Electronic case report form

EDC Electronic data capture

EMEA Europe, Middle East and Africa

GCP Good clinical practice

ICF Informed consent form

IEC Independent ethics committee

IRB Institutional review board

ISOIWRS International Organization for Standardization

IWRS Interactive Web Response System

MedDRA Medical Dictionary for Regulatory Activities

NE Nocturnal enuresis

NICE National Institute for Clinical Excellence

PCP Primary care provider

PDSS Paediatric Daytime Sleepiness Scale

PinQ Paediatric Incontinence Questionnaire

PRO Patient-reported outcome

PT Preferred term

QoL Quality of life

SAE Serious adverse event

SAP Statistical analysis plan

SD Standard deviation
SOC System organ class

TEAE Treatment-emergent adverse event

USADE Unanticipated serious adverse device effect WHOQoL World Health Organization Quality of Life

# **Study Synopsis**

Full Stud	y Title: Effect of use of DryNites® absort	ent pants or	n the rate of spontaneous resolution of
paediatric	nocturnal enuresis (NE)	_	-
Phase	Phase IV	Type:	Clinical Investigation

Phase:	Phase IV	Type:	Clinical Investigation
Number of Patients: 120		Duration of Patient Participation :	
		8 weeks (p	orimary endpoint) – optional extension
		of 4 weeks	
Number o	f Sites : 7-12	Duration	of Study: 3 years

# **Background and Rationale:**

Nocturnal enuresis (NE) is stressful for both children and their parents/carers. Children vary in the age at which they achieve night-time dryness; in almost all cases, children will stop bed-wetting without any need for treatment. Use of absorbent pants for the management of NE is a controversial area, with many groups expressing conflicting opinions on the issue. Some experts believe that the use of absorbent pants can prevent the child from learning night-time bladder control, while others believe it has no impact on the rate at which children become dry. This study aims to show that using DryNites® absorbent pants in children with monosymptomatic NE does not have a negative effect on the speed that children become dry, compared with removing absorbent pants. It also aims to show that using DryNites® improves the overall quality of life (QoL) and sleep quality of both children and their parents/carers.

# **Objectives**:

Primary objective: to determine if discontinuing the use of DryNites® absorbent pants over a period of 4 weeks has any impact on the rate of spontaneous resolution of NE compared with continuing use of DryNites® absorbent pants.

# Secondary objectives:

- To determine if using DryNites® absorbent pants improves the child's QoL assessed by the Paediatric Incontinence Questionnaire (PinQ) compared with not using absorbent pants
- To determine if using DryNites® absorbent pants improves the parent/carer's QoL assessed by the World Health Organization Quality of Life BREF (WHOQoL-BREF) compared with not using absorbent pants
- To determine if using DryNites® absorbent pants improves the child's sleep assessed by the Paediatric Daytime Sleepiness Scale (PDSS) compared with not using absorbent pants
- To determine if using DryNites® absorbent pants improves the parent/carer's sleep assessed by the Checklist Individual Strength questionnaire (CIS) compared with not using absorbent pants

Full Study	Full Study Title: Effect of use of DryNites® absorbent pants on the rate of spontaneous resolution of				
paediatric nocturnal enuresis (NE)					
Phase:	Phase IV	Type:	Clinical Investigation		
Number of Patients: 120		Duration of Patient Participation:			
		8 weeks (primary endpoint) – optional extension			
		of 4 weeks			
Number o	Number of Sites: 7-12				
To dete	• To determine if DryNites® absorbent pants offer different benefits or limitations to previously used				

• To determine if DryNites® absorbent pants offer different benefits or limitations to previously used absorbent pants/nappies.

# Study design:

This is an 8-week randomised, open-label, 2-arm, parallel-group Phase IV trial with a 2:1 allocation ratio for discontinuation or continuation of use of DryNites® absorbent pants in children with NE, and an optional 4-week extension period. This will be an equivalence trial for the primary endpoint.

Eligible patients are children with a clinical diagnosis of monosymptomatic NE, not previously treated for NE, and managed with absorbent pants/nappies (any brand) for a minimum of 6 months. Participants must be dry at day for at least 6 months. Participants will be divided in 2 age groups of similar size  $(4-<6 \text{ years and } \ge 6-8 \text{ years old})$ .

The study consists of 3 consecutive periods of 4 weeks each, including the run-in, the intervention (core trial) period, and the extension period. During the 4-week run-in period, all participants will be assigned to using DryNites® every night. Participants meeting the inclusion criterion of NE 7 nights per week during the last week of the run-in period will be randomised in the intervention (core trial) period. During the 4-week intervention period, participants will be assigned to either stopping the use of absorbent pants or continuing DryNites® in a 2:1 ratio. All participants will receive absorbent bed mats to use every night, however, the use of bed mats is optional. During the 4-week optional extension period, participants will remain on their randomly assigned treatment for an additional 4 weeks.

Study specific mandated clinic or remote visits will be required as part of the participation in this study. Participants will be reimbursed for their travel expenses for on-site visits. Participants will be assessed on Day 0 (baseline), Day  $28 \pm 7$ days (end of run-in and randomisation), Day  $56 \pm 7$ days (end of intervention/core trial period), and Day  $84 \pm 7$ days (end of extension period). As a contingency to the restrictions due to the Covid-19 outbreak, the baseline, randomisation, and any subsequent visit (i.e., Visits 3 and 4) can also be performed remotely in case the patient cannot visit the site in person.

Dry and wet nights will be captured every day from the start of the run-in period to discontinuation of the study through an electronic diary, accessible through the parent's/carer's own device (smart phone, tablet, or computer).

QoL and sleep questionnaires will be completed in electronic format either on-site during the clinic visits or after the visit from randomisation onwards, using the parent's/carer's own electronic device. The perception of DryNites® attributes, compared to previously used absorbent products will be evaluated

through 2 specific questionnaires designed for this study, at study entry (for previous absorbent pants/nappies) and at the end of the run-in period (for DryNites®).

# Study population:

The study will aim to randomise approximately 120 participants aged 4-8 years from a total of 7-12 sites in 3 countries (Belgium, Denmark, and the United Kingdom) over a 30-month enrolment period. Children/parents/carers actively seeking help for NE can be recruited via specialist centres, clinician visits, referrals, and collaboration with primary care providers.

#### **Inclusion criteria**

The following criteria must be met for the participant to be enrolled in the study:

- 1. Aged between 4-8 years at the time of enrolment
  - a. To be categorised in the younger participant group, participants must be aged 4-<6 years
  - b. To be categorised in the older participant group, participants must be aged ≥6-8 years
- 2. Have a clinical diagnosis of monosymptomatic primary NE
- 3. Have been dry in the day for  $\geq$ 6 months prior to enrolment
- 4. Have on average no more than 1 dry night per month during the past 6 months at enrolment
- 5. Using absorbent pants/nappies to manage NE for at least 6 months prior to enrolment
- 6. Have an informed consent form (ICF) signed by their parent(s)/carer(s)
- 7. For randomisation: have NE 7 nights per week over Week 4/last week of the run-in period

#### **Exclusion criteria**

Patients meeting ANY of the following criteria are not eligible for participation:

- 1. Children in foster/court care
- 2. Have implemented any previous intervention to address NE (use of prescribed alarm schedule, desmopressin, imipramine, anticholinergics), or withdrawal of pants/nappies for >7 days in the previous 6 months
- 3. Have secondary NE
- 4. Have wetting in the day
- 5. Have faecal soiling
- 6. Have known urinary tract disease
- 7. Have diabetes

Full Study Title: Effect of use of DryNites® absorbent pants on the rate of spontaneous resolution of			
paediatric i	nocturnal enuresis (NE)		
Phase:Phase IVType:Clinical Investigation			
Number of Patients: 120		Duration of Patient Participation :	
		8 weeks (p	rimary endpoint) – optional extension
		of 4 weeks	
Number of	f Sites: 7-12	Duration	of Study: 3 years

- 8. Receive any regular intake of medication
- 9. Have a known developmental/neurological disorder
- 10. Have links to Kimberly-Clark of any kind (including family relations employed by Kimberly-Clark, holding stocks or shares in Kimberly-Clark)

#### Data collection/Data Sources:

Participants will be assessed on Day 0 (baseline), for demographics, height and weight, medical history, concomitant medication, prior use of absorbent pants/nappies, and full physical examination (optional). In case of remote visit, height and weight and full physical examination will be done when the visit is performed on-site. At Day 28 ± 7days (end of run-in and randomisation), Day 56 ± 7days (end of intervention/core trial period) and Day 84 ± 7 days (end of extension period), participants will be assessed for adverse events (AEs) since the previous visit, concomitant medication used to treat AEs, and patient-reported outcome (PRO) questionnaires. Baseline, randomisation, and any subsequent visit could be performed remotely via phone or video/teleconference, if an on-site visit cannot be performed. For remote visits, PRO questionnaires will be accessed through the parent's/carer's own electronic device and study materials (i.e., DryNites®, bed mats) will be shipped to the patient. The PRO questionnaires will be available after a given visit (and should be completed before the next visit). The PRO questionnaires can also be completed remotely, within the same time window, if completion is not feasible during any on-site visit including baseline. Dry and wet nights will be captured every day from the start of the run-in period to discontinuation of the study through an electronic diary, accessible through the parent's/carer's own device (smart phone, tablet, or computer).

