# 4.3.5. Methods for Assigning Patients to Treatment Groups

A patient randomisation list will be produced using permuted block randomisation stratified by age group (4–<6 years old and  $\ge6-8$  years old) and a 2:1 group allocation for discontinuation or continuation of the use of DryNites® pyjama pants.

When a patient is qualified for entry into the randomised treatment period, treatment assignment will be performed by means of an IWRS on a central level on Visit 2 (Day  $28 \pm 7$  days).

Before the study is initiated, the log in information and directions for the IWRS will be provided to each study centre.

The Investigator or his/her delegate (study coordinator) will log on to the EDC and confirm that the patient fulfils the eligibility criteria and proceed with the randomisation. Participants will be assigned a unique number (randomisation number) in ascending numerical order on the next available record in the group at each study centre. The randomisation number encodes the participant's assignment to 1 of the 2 arms of the study (No Pants arm or DryNites® arm).

The treatment assignment (Discontinuation vs. continuation of DryNites®) will be captured in the EDC from the IWRS.

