7. GENERAL CONSIDERATIONS

Continuous variables will be reported as mean (and standard deviation [SD]) along with median and range where appropriate.

The minimum and maximum will be reported to the same number of decimal places as the raw data recorded in the database. The mean and median will be reported to 1 decimal place while the SD will be reported to 2 decimal places.

Categorical variables will be summarised as number and proportion of the total study population, and by age subgroups (4–<6 years and \geq 6–8 years) where appropriate.

In general, descriptive statistics of quantitative parameters (result and change from baseline) by scheduled visits will be provided on observed cases, that is, patients having non-missing assessments at a specific visit. Percentages will then not include the missing category, but the count of missing observations will be provided. Percentages will be presented to 1 decimal place except percentages equal to 100 that will be presented as 100% and zero frequencies that will be presented as 0%.

Confidence intervals (CI) and statistical tests will be 2-sided unless otherwise specified. P-values, which are greater than or equal to 0.0001, and less than or equal to 0.9999, will be presented to 4 decimal places. All other p-values, which are less than 0.0001, will be presented as <0.0001. Individual patient data will be presented in listings considering the Screened Set.

Document:	Y:\Kimberly-Clark\DryNites\Documentation\SAP\DryNites_SAP_v1.0_20200203		
Author:	[name] Version Number:		
		Version Date:	03Feb2020
Template No.:	RWI_TP_BIOS0013 Revision 1		Reference: RWI_WI_BIOS0015

Effective Date: 15Jun2018

Descriptive analyses will be performed on the SCR Set and the RND Set to gain an understanding of the qualitative and quantitative nature of the data collected and the characteristics of the sample studied. If more than 15% of randomised participants will be excluded from the PAS, the baseline descriptive analysis will be repeated on the primary endpoint analysis population.

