7.1 Reference Start Date

Reference start date is defined as the day of the randomisation and will appear in every listing where an assessment date or event date appears.

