7.3 Windowing Conventions

The following table describes assignment of visit windows to the following data for purposes of analysis:

Table A:Windowing

Assigned Study Day (Inclusive)		Visit Assigned	
From	То		
-35	0	Visit 1	
1	1	Visit 2	
2	42	Visit 3	

Template No.: RWI_TP_BIOS0013 Revision 1

Reference: RWI_WI_BIOS0015

Effective Date: 15Jun2018

43 63 Visit 4

To define cut on visits to the patient's diary, visit date will be used as reference along with windowing conventions.

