15.3 Exploratory Analysis

Effective Date: 15Jun2018

The exploratory analysis will include the refresh of the analysis on patient disposition, primary and secondary analysis and adverse events, including the data collected over the extension period. A repeated measure model will be presented to assess the extension period effects on PinQ, WHOQoL-BREF, PDSS and CIS questionnaires.

Repeated measure model will be handled with mixed effects models using SAS PROC MIXED with an unstructured correlation matrix to model the within-patient errors, unless the model does not converge, in which case the heterogeneous Toeplitz covariance structure followed by the heterogeneous first-order autoregressive covariance structure will be checked. Parameters will be estimated using the Newton-Raphson algorithm. Denominator degrees of freedom will be estimated

Document:	Y:\Kimberly-Clark\DryNites\Documentation\SAP\DryNites_SAP_v1.0_20200203		
Author:	[name]	Version Number:	1.0
		Version Date:	03Feb2020
Template No.:	RWI_TP_BIOS0013 Revision 1		Reference: RWI_WI_BIOS0015

using the Kenward-Roger approximation by fitting values from post-randomisation scheduled visits. This likelihood-based approach is tolerant of missing data provided that they are MAR. Missing at random assumes that the missing values are systematically related to other, measured covariates and that no unmeasured related covariates exist.

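### SAP Table A ends Visit 4 at study day 63, but a protocol-compliant Visit 4 can fall as late as study day 71, and no rule covers the gap

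*Protocol*

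**What the plan says.** **SAP.** Section 7.1 sets the origin: "Reference start date is defined as the day of the randomisation". Section 7.3 introduces Table A with "The following table describes assignment of visit windows to the following data for purposes of analysis", although no list of data follows. The table gives Visit 1 study days -35 to 0, Visit 2 day 1, Visit 3 days 2 to 42 and Visit 4 days 43 to 63. There is no later row and no rule for data outside all rows. For the diary the section adds "To define cut on visits to the patient's diary, visit date will be used as reference along with windowing conventions".

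Section 7 says that descriptive statistics "by scheduled visits will be provided on observed cases, that is, patients having non-missing assessments at a specific visit". Section 15.3 says "A repeated measure model will be presented to assess the extension period effects on PinQ, WHOQoL-BREF, PDSS and CIS questionnaires", and fits that model to values from scheduled visits after randomisation.

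**Protocol.** Visits are counted from baseline, Day 0. Section 4.3.5 states that "treatment assignment will be performed by means of an IWRS on a central level on Visit 2", at Day 28 ± 7. Section 4.1, the schedule of assessments (Table 2) and the synopsis put the end of the extension at Day 84 ± 7: "Day 84 ± 7 days (end of extension period), participants will be assessed for adverse events (AEs) since the previous visit". The synopsis sentence goes on to include the questionnaires. On their timing for remote visits the synopsis says "The PRO questionnaires will be available after a given visit (and should be completed before the next visit", and nothing is scheduled after Visit 4.

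**The concern.** The two documents count from different origins, and randomisation may itself move by a week either way. A window counted from randomisation has to absorb the tolerance of both visits. The Visit 4 upper limit does not.

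A family that keeps every protocol window can therefore complete the end-of-extension questionnaires on a day that Table A assigns to no visit. Visit 4 is the only assessment scheduled at the end of the extension, so no later form can stand in. At stake are the completeness of the exploratory extension results, and whether the handling of such forms is fixed in advance or left to whoever programs the tables.

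**Working it through.** **Inputs**
- Randomisation (Visit 2): protocol Day 28 ± 7, so Day 21 to 35 (Protocol 4.3.5).
- Visit 3: protocol Day 56 ± 7, so Day 49 to 63 (Protocol 4.1, Table 2).
- Visit 4: protocol Day 84 ± 7, so Day 77 to 91 (same places).
- SAP Table A: Visit 2 is study day 1; Visit 3 is days 2 to 42; Visit 4 is days 43 to 63.

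**Formula.** Because Table A makes randomisation study day 1, study day = protocol day of visit - protocol day of randomisation + 1. With e2 and e4 the deviations of Visits 2 and 4 from nominal, each from -7 to +7:

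study day of Visit 4 = (84 + e4) - (28 + e2) + 1 = 57 + e4 - e2

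**Reproducing the SAP's 63.** It comes out as 91 - 28 = 63, which is elapsed days with randomisation exactly on Day 28. On Table A's own count, the same child is on study day 64. The Visit 3 limit of 42 comes out as 63 - 21 = 42, which is elapsed days with randomisation at its earliest. On these derivations the two upper limits rest on different assumptions; the SAP does not explain either.

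**Range of a compliant Visit 4**
- Earliest: 77 - 35 + 1 = 43, equal to the lower limit of the row.
- Nominal: 84 - 28 + 1 = 57, well inside.
- Latest: 91 - 21 + 1 = 71, which is 8 days past 63.

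| Randomised on protocol Day | Latest compliant Visit 4 (study day) |
|---|---|
| 21 | 71 |
| 24 | 68 |
| 28 | 64 |
| 29 | 63 |
| 35 | 57 |

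So the gap can arise for any child randomised on or before Day 28, and for none randomised later.

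**How many day combinations are affected.** There are 15 × 15 = 225 in-window pairs. Visit 4 falls after day 63 when e4 - e2 ≥ 7, which gives 8 + 7 + 6 + 5 + 4 + 3 + 2 + 1 = 36 pairs, and 36/225 = 16%.

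**Variants**
- Elapsed days (no + 1): the range is 42 to 70. Pairs after 63 need e4 - e2 ≥ 8, giving 7 + 6 + 5 + 4 + 3 + 2 + 1 = 28, and 28/225 = 12.4%.
- Visit 4 booked 56 ± 7 days from actual randomisation: study days 50 to 64, so only day 64 is outside, 1 day in 15 (about 7%). On elapsed days the latest is 56 + 7 = 63 and nothing is outside.

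**A related edge.** A Visit 3 on Day 63 after randomisation on Day 21 is on study day 63 - 21 + 1 = 43, which Table A labels Visit 4. It is the only one of the 225 in-window Visit 2/Visit 3 pairs to pass day 42.

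**The case against.** The strongest reply is that nothing need be lost. The SAP nowhere says that data outside a window are excluded. Table A's introduction does not list the data it governs. The questionnaires are collected at named visits, and both SAP 7 and SAP 15.3 speak of scheduled visits. A programmer who uses the nominal visit from the eCRF would keep every form. This stands in part: exclusion is the result of applying Table A literally, not a stated rule. But a table offered as the visit assignment for analysis, with no provision for what falls outside it, leaves the choice open.

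A second reply is that 63 may be a deliberate window of 56 + 7 days from randomisation. That is possible, but SAP 4.3, which lists changes from the protocol, mentions no narrowing.

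A reader might also infer more than the documents support:
- **That 16% of children would be lost.** It is a share of possible day pairs. Reading it as a patient proportion would need independent, uniform visit timing, for which the documents give no basis.
- **That the loss would be selective.** Nothing in the documents links attending a few days late to outcome.
- **That forms completed late from home would add materially.** Completion after the visit is allowed, but Protocol 4.1 asks for it as close to the visit as possible, and no figure is given.
- **That diary data would be lost too.** The diary cut uses the actual visit date together with the windows, so the effect is unclear.
- **That the main results are at risk.** The primary and secondary endpoints are at Day 56. Treatment-emergent adverse events are bounded by the end of the extension (SAP 16.1), and Extension Set membership is by participation (SAP 6.5). None of these depends on the Visit 4 upper limit.

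**Conclusion.** The point holds as a mismatch between SAP Table A and the protocol's visit schedule. Table A stops at study day 63; a compliant Visit 4 can reach day 71, or 70 if days are counted as elapsed. It does not need the extreme case: on Table A's count, randomisation on Day 28 with Visit 4 on Day 91 already gives day 64.

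The consequence is limited to forms dated study days 64 to 71 in exploratory extension output, and it follows only if Table A is applied literally. The size cannot be stated as a number of patients: the illustrations run from 36 of 225 day pairs down to 1 day in 15, and to none if Visit 4 is booked from randomisation and days are counted as elapsed.

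The conclusion assumes that both protocol tolerances are measured from baseline Day 0, as the visit days imply. The SAP cites plan version 1.0 and the protocol supplied is version 3.0, but the amendment log shown lists no change to the visit days. The correction is worth making because it is cheap and removes a choice that would otherwise be made after the data are in.

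**What to change.** In SAP 7.3, Table A:
- Extend the Visit 4 upper limit to at least study day 71, or leave that row open-ended for children in the Extension Set.
- State that the nominal (eCRF) visit governs for scheduled-visit questionnaires, including Visit 4 forms completed after the visit. This also keeps the compliant Visit 3 on study day 43 from being labelled Visit 4, which a wider Visit 4 row alone would not do.
- Say what happens to data outside every window, and whether the windows restrict the diary cut or the visit date alone decides it.

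The cost is one table cell and a few sentences in the SAP, with no new data and no protocol amendment. The downside is that a few late forms widen the spread of assessment times slightly.

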#### 4.7.3. Visit 2 - End of Run-in/Randomisation Visit

The following assessments will be performed for all patients at end of run-in/randomisation visit (Day  $28 \pm 7$ ):

- Any AEs occurred since the baseline visit
- Concomitant medications for AEs
- Review of diary data
- DryNites® Clinical Trial Questionnaire (all participants)
- Patient and parents/carers QoL and sleep questionnaires: PinQ, WHOQOL, PDSS,
   CIS (for randomised participants only)

The Investigator will confirm NE frequency by assessing the data recorded in the diary by the participants/parents/carer at the randomisation visit (Day  $28 \pm 7$ ). Only participants who experience NE at a frequency of 7 nights per week during the last week of the run-in period (no dry night) will be randomised.

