#### **5.4.2.** Planned Analyses

The total number of patients included in each analysis set along with the number of patients for each of following categories will be provided as disposition analysis:

- Patients consented, overall and by age group  $(4-<6 \text{ years and } \ge 6-8 \text{ years})$
- Patients randomised, overall and by age group  $(4-<6 \text{ years and } \ge 6-8 \text{ years})$
- Patients who completed the 4-week intervention period, overall and by age group  $(4-<6 \text{ years and } \ge 6-8 \text{ years})$
- Patients who entered the extension period, overall and by age group (4–<6 years and  $\ge$ 6–8 years)
- Patients who completed the extension period, overall and by age group (4-<6 years) and  $\ge 6-8 \text{ years})$
- Time and reasons for discontinuation of the study, overall and by age group  $(4-<6 \text{ years and } \ge 6-8 \text{ years}).$

For all categories except the Screened Set, the percentages will be calculated using the number of randomised patients as the denominator for each treatment group.

Baseline will be defined as the data collected at or prior to randomisation; demographic and baseline characteristics, disease history, physical examination, medical history and concomitant medication will be summarised with appropriate descriptive statistics by group and separately for age subgroups.

These summaries will be provided for the Screened and Randomised Sets.

Body height, body weight and BMI will be summarised. The calculated BMI will be classified as follows based on comparison with:

- Underweight (<5th percentile for sex and age),
- Normal (from 5th to less than 85th percentile for sex and age),
- Overweight (from 85th to less than the 95th percentile for sex and age),
- Obese ( $\geq 95^{th}$  percentile for sex and age).

Physical examination will be summarised as percentage of patients with normal/abnormal result overall and as per the physical examination features listed in Section 4.5.3.2.

Pathologies associated with past medical or surgical history will be summarised by primary SOC and PT as per MedDRA. Concomitant therapies will be summarised by Anatomical Therapeutic Chemical (ATC) Classification System.

Direct- to-patient data will be analysed descriptively at each assessment along with applicable change from baseline on the Randomised Analysis Set and Primary Analysis Set.

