4.3 Changes to Analysis from Protocol

Concomitant medications will be collected in relation to adverse events and medical device incidents only. For this reason, the summary of concomitant medication will be provided on randomised analysis set only as no data will be collected for patients screened and not randomised.

Document:	Y:\Kimberly-Clark\DryNites\Documentation\SAP\DryNites_SAP_v1.0_20200203		
Author:	[name] Version Number:		1.0
		Version Date:	03Feb2020
Template No.: RWI_TP_BIOS0013 Revision 1			Reference: RWI_WI_BIOS0015
Effective Date: 15Jun2018			

Safety set definition will be modified to include all patients exposed to DryNites for at least 1 night after signature of informed consent.

Treatment emergent adverse events will be defined as all events occurred or worsened in severity after the start of the screening period.

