6.3 Safety Analysis Set

The safety analysis set (SAF) will contain all patients exposed to DryNites® for at least 1 night after signature of informed consent.

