13. MEDICATIONS

Only medications administered to treat an AE or MDI will be collected and will be considered all concomitants.

Therapies will be presented for the SAF set and coded using Anatomical Therapeutic Chemical (ATC) Classification System.

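### SAP 4.3 and SAP 13 put the AE-medication summary on different analysis sets, and the reason SAP 4.3 gives conflicts with the protocol's data collection

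*Protocol*

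**What the plan says.** **SAP.** Section 4.3, which declares changes from the protocol, notes that medication is recorded only in connection with AEs and medical device incidents (MDIs). It concludes that "the summary of concomitant medication will be provided on randomised analysis set only", giving as the reason "as no data will be collected for patients screened and not randomised". Section 13 covers the same records and states: "Therapies will be presented for the SAF set". Section 6.3 defines that set as "all patients exposed to DryNites® for at least 1 night after signature of informed consent".

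**Protocol, collection.** Section 4.7.1 lists AE medication, where relevant, among the Visit 1 assessments for every consented child. Section 4.7.3 opens with "The following assessments will be performed for all patients at end of run-in/randomisation visit" and includes medication for AEs. Section 4.7.6 collects it from all enrolled children at discontinuation. Table 2 marks it at every visit. The synopsis, for Days 28, 56 and 84, names "concomitant medication used to treat AEs, and patient-reported outcome (PRO) questionnaires".

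**Protocol, analysis.** Section 5.4.2 includes concomitant medication with the baseline summaries and says: "These summaries will be provided for the Screened and Randomised Sets". SAP 4.3 openly replaces that choice.

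**The concern.** The two SAP sections give the programmer incompatible populations for one set of records. The reason offered for the narrower population is that the data will not exist, yet the protocol instructs sites to collect them.

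This bears on safety reporting. Every child who enters the run-in is assigned DryNites nightly, protocol section 2 says the product's side-effects have not been studied, and protocol 7.1.5 requires relatedness to DryNites to be assessed for run-in AEs. Suppose a child develops a rash in the run-in, is treated for it, and then fails the seven-wet-nights check. The rash is counted in AE tables built on the Safety Set. Under SAP 4.3 the treatment is left out of the medication table, and the two tables have different denominators.

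**Working it through.** No formula applies, and the plan gives no figure to reproduce. The check sets the sections side by side.

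1. **Is there one table or two?** SAP 4.3 and SAP 13 both say that only medication linked to an AE or MDI is collected. There is therefore one body of data, and the sections cannot be read as describing separate summaries.

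2. **Do the two populations differ?** The SAP 4.3 population is children assigned to a randomisation group (SAP 6.2). The SAP 13 population is children with at least one night of DryNites after consent (SAP 6.3). A child who wears DryNites in the run-in and is not randomised belongs to the second and not the first.

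3. **Does the reason in SAP 4.3 agree with the protocol?**
   - Visit 1: AE medication, all consented patients (4.7.1).
   - Visit 2: AE medication, all patients (4.7.3). In the same list, only the QoL and sleep questionnaires are limited to randomised participants.
   - Discontinuation: AE medication, all enrolled patients (4.7.6). Here too, only the questionnaires carry a randomised-only condition.
   - Table 2: AE medication is marked at Visits 1 to 4 and at end of study. The QoL/sleep row has footnote (f), limiting it to children who meet the randomisation criterion; the medication row has no such footnote.
   - AEs are collected from consent (4.6.1). Limiting medication to AE treatment therefore does not imply that non-randomised children have none.

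   The protocol restricts items to randomised children where it means to, and it does not do so for AE medication.

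4. **What would be lost under SAP 4.3?** The restriction is by set and not by time. Run-in medication of a child who is later randomised stays in the summary under either section. Only the medication of exposed, never-randomised children drops out.

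5. **Where would those data still appear?** SAP section 7 presents individual data in listings on the Screened Set, so the records would be listed if they were captured. The AEs stay in the Safety Set outputs (SAP 16), with TEAEs counted from the start of screening (SAP 16.1).

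6. **A possible origin, by inference only.** In protocol Table 4 the Safety Analysis Set is the Randomised Set, and on that definition SAP 4.3 and SAP 13 would agree. SAP 4.3 itself widens the Safety Set in its next paragraph, and the medication sentence may simply not have been updated to match.

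**The case against.** The strongest reply is that SAP 4.3 is a disclosed change and that its authors may have known what the CRF holds. The SAP is based on plan version 1.0 and CRF version 1.0; neither is available here, and the protocol reviewed is version 3.0. Protocol 4.3.4 gives a minimal dataset for screen failures, defined as consented but not randomised, and that dataset does not name medication. It could explain the SAP sentence. SAP 13 already names the wider set, individual listings remain, and the summaries are descriptive.

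Much of this stands. The departure from protocol 5.4.2 is declared, so the live conflict is between two SAP sections; counting protocol 5.4.2 as a third competing population would overstate it. A reader might also infer that the SAP's reason is simply untrue. The documents do not go that far: they show that it conflicts with the protocol's visit instructions, and only the CRF can show what is captured. A minimum dataset, however, does not cancel the explicit collection in 4.7.1, 4.7.3 and 4.7.6.

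A reader might infer that all run-in treatment is lost. It is not, because later-randomised children keep theirs.

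A reader might also try to size the gap from the sample-size assumption: 1 − 0.95^7 = 1 − 0.698 = 30.2% fail the first check, and 0.302² = 9.1% fail twice if all are re-screened. That does not hold. The 0.95 is the assumed risk in the continuation arm in the last intervention week, not a run-in rate. The entry limit of about one dry night a month, taken as 1 in 30, gives 1 − (29/30)^7 = 21% and, squared, 4.5%. Both versions assume independent nights and weeks, and both count children rather than treated AEs. The plan's own allowance, 15/60 = 25%, pools screen failures with dropout and poor compliance.

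**Conclusion.** The point holds as a minor inconsistency that needs correcting. SAP 4.3 and SAP 13 specify different populations for the same AE/MDI medication summary, and the reason in SAP 4.3 is at odds with the protocol. If SAP 4.3 is followed, the summary omits AE medication of children exposed in the run-in and never randomised, while their AEs are counted.

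The size cannot be derived: neither document gives an AE rate, a treatment rate or a separate screen-failure rate. It would be going too far to say that the treatment burden on the device is shown to be understated. The primary analysis, the secondary endpoints and the comparison between arms are unaffected.

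The conclusion assumes that sites follow the visit instructions in protocol 4.7. If the CRF does not capture AE medication before randomisation, the listings would not hold those records either, and the problem becomes one of data capture.

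**What to change.** - In SAP 4.3, delete the Randomised Set restriction on the medication summary and the reason given for it.
- Keep SAP 13: summarise AE and MDI medication on the Safety Analysis Set. Show never-randomised children in a separate run-in column, since they have no arm.
- Check that the CRF captures AE medication before randomisation, including for children who become screen failures, given the minimal dataset in protocol 4.3.4.

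The cost is an edit to the SAP 4.3 text, one table shell and one CRF check. If the CRF follows protocol 4.7, no new data are needed; if it does not, the gap should be stated in the SAP and the study report.
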